7.5. Preparation/Handling/Storage/Control

1. The investigator or designee must confirm appropriate temperature conditions have been maintained during transit for all study treatment received and any discrepancies are reported and resolved before use of the study treatment.
2. Only participants enrolled in the study may receive study treatment and only authorized site staff may supply or administer study treatment. All study treatments must be stored in a secure, environmentally controlled, and monitored (manual or automated) area in accordance with the labeled storage conditions with access limited to the investigator and authorized site staff.
3. The investigator, institution, or the head of the medical institution (where applicable) is responsible for study treatment accountability, reconciliation, and record maintenance (ie, receipt, reconciliation, and final disposition records).
4. Further guidance and information for the final disposition of unused study treatment are provided in the Study Reference Manual

7.6. Treatment Compliance

Subjects will be intramuscularly injected the product at a medical institution. The injection will be recorded in the source documents, and described in the case report form.

7.7. Concomitant Therapies

The medications that are used by subjects at the time of enrolment in the study or all medications and vaccines to be used during the study (over the counter drugs or prescribed drugs, vitamins, and/or herbal supplements) must be recoded with the following items:

- Reasons for use
- Initial date of administration and administration dates, including completion day
- Regarding the dose, including dosage and number of administration

Contact the medical monitor if there are any questions about concomitant therapies or preceding drugs.

7.7.1. Permitted Concomitant Drugs/Therapies

Following drugs and therapies are permissible only if a subject is already using them before initiation of the study. However, the dosage and administration will not be changed from the screening through completion of the blind phase. In and after open-label phase, dose reduction and discontinuation of the drugs will be allowed. However, once dose is decreased, re-increase will not be performed. If the drug(s) is/are discontinued, the drugs cannot be resumed. No new treatment will not be started after screening phase.

- Central muscle relaxants
(baclofen, tizanidine hydrochloride, eperisone hydrochloride, chlorphenesin carbamate, afloqualone, etc.)
- Tetracycline antibiotics
(tetracycline hydrochloride, doxycycline hydrochloride, minocycline hydrochloride, etc.)
- Anticholinergics
(butylscopolammonium bromide, trihexyphenidyl hydrochloride, etc.)
- Benzodiazepines
(diazepam, etizolam, etc.)
- Benzamides
(tiapride hydrochloride, sulpiride, etc.)
- Antiepileptic drugs
(phenytoin, etc.)
- Intrathecal baclofen therapy

Rehabilitation therapies such as physical therapy, occupational therapy, and static splint are permissible. However, in the blind phase, the frequency and regimens (description of the therapy and intensiveness) for the upper limb, which involves in the study will not be changed. In addition, in the open-label phase, changing rehabilitation therapy to another one that seems to be the most appropriate for a subject is permissible based on the degree of improvements in spasticity. In such cases, the information will be described on CRF. Rehabilitation therapy will not be given on the day of investigational product injection.

Appropriate rehabilitation therapies should be selected from among the following: task-specific training, muscle strengthening exercise, stretching/range of motion (ROM) exercise, splints and orthoses, taping, positioning aid, and others (specify). As for the frequency, the number of days per month, when rehabilitation therapies were performed, between V1 and V5 will be calculated, and the most appropriate frequency will be selected from among the following: not performed, ≤ 8 days per month, > 8 and ≤ 16 days per month, > 16 and ≤ 24 days per month, and > 24 days per month. Details will be provided in the study reference manual (SRM).

7.7.2. Contraindicated Medications/Therapies

Following drugs and therapies will be prohibited to use from screening phase through completion of the study:

- Botulinum toxin preparations
- Peripherally acting muscle relaxants
- (dantrolene sodium, suxamethonium chloride, pancuronium bromide, vecuronium bromide, rocuronium bromide)
- Antibiotic agents with neuromuscular junction blocking effects
 - Aminoglycosides (streptomycin sulfate, kanamycin sulfate, gentamicin sulfate, neomycin sulfate, spectinomycin hydrochloride, etc.)
 - Polypeptides (polymyxin B sulfate)
 - Lincomycins (lincomycin hydrochloride, clindamycin)
 - Enviomycin sulfate
- Nerve blocks such as phenol block, ethanol block and MAB for the upper limb
- Surgical cast or a dynamic splint
- A surgery for the upper limb
- A surgical cast or a dynamic splint for the upper limb
- Corticosteroid injection or an anesthetic agent for the upper limb
- Ultrasound therapy, TENS (transcutaneous electrical nerve stimulation), electrical stimulation therapy, or acupuncture therapy for the upper limb

Following drugs and therapies will be prohibited to use from screening phase through completion of the blinded-phase:

- CIMT (constraint-induced movement therapy)

7.8. Treatments after Completion of the Study

The investigator will take responsibility for subject's medical care after completion of the study, whether the sponsor provides a certain treatment or not.

8. DISCONTINUATION CRITERIA

8.1. Discontinuation of Study Treatment

The efficacy of the investigational product used in this study sustains for about 3 to 4 months following a single dose, and thus daily dosage is not required; accordingly, treatment discontinuation shall not be defined in this study, and will be considered to be identical to subject withdrawal from this study.

8.2. Withdrawal from the Study

- A participant may withdraw from the study at any time at his/her own request, or may be withdrawn at any time at the discretion of the investigator for safety, behavioral, compliance or administrative reasons.
- If the participant withdraws consent for disclosure of future information, the sponsor may retain and continue to use any data collected before such a withdrawal of consent.
- If a participant withdraws from the study, he/she may request destruction of any samples taken and not tested, and the investigator must document this in the site study records.
- A subject discontinuing this study must visit the study site for study termination assessment promptly upon decision to discontinue the study.
- Refer to the schedule of assessment (SoA), completion visit (FV), for the details of data to be collected at the study discontinuation, and additional assessment that must be completed.

8.2.1. Liver Chemistry Stopping Criteria

[figure not shown]
A set of criteria for **study discontinuation and follow-up investigation based on hepatic function test** (in reference to FDA premarketing clinical liver safety guidance) is specified herein to ensure the safety of subjects and to evaluate the causes of hepatic events. The guidelines related to this protocol are based on the FDA premarketing clinical liver safety guidance:

<http://www.fda.gov/downloads/Drugs/GuidanceComplianceRegulatoryInformation/Guidances/UCM174090.pdf>.

The investigator should consider discontinuing the study treatment upon discovery of liver function test abnormal, and if the subject is applicable to any of the symptoms presented in the algorithm, or such discontinuation is determined to be the best choice for the subject as judged by the investigator.

Algorithm A: Phase III-IV Liver Chemistry Stopping and Increased Monitoring Algorithm

[figure not shown]
Algorithm A: Phase III-IV Liver Chemistry Stopping and Increased Monitoring Algorithm

Liver Safety Required Actions and Follow up Assessments Section can be found in Appendix 6.

Algorithm B: Phase III-IV Liver Chemistry Increased Monitoring Algorithm with Continued Therapy for ALT $\geq 3xULN$ but $< 8xULN$

Algorithm B: Phase III-IV Liver Chemistry Increased Monitoring Algorithm with Continued Therapy for ALT $\geq 3xULN$ but $< 8xULN$

Liver Safety Required Actions and Follow up Assessments Section can be found in Appendix 6.

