12.6. APPENDIX 6: Liver Safety Required Actions and Follow up Assessments

In order to secure the subject's safety and evaluate the causes of liver event, **the criteria for discontinuation and follow-up based on the liver function test values in the phase III-IV studies** will be stipulated.

Criteria for discontinuation based on the liver function test values in the phase III-IV studies and necessary follow-up

Criteria for discontinuation based on the liver function test values	
ALT	ALT \geq 8xULN
ALT increase	ALT \geq 5xULN but <8xULN persists for \geq 2 weeks ALT \geq 3xULN but <5xULN persists for \geq 4 weeks
Bilirubin ^{1,2}	ALT \geq 3xULN and bilirubin \geq 2xULN (>35% direct bilirubin)
INR ²	ALT \geq 3xULN and INR>1.5, if INR measured
Cannot Monitor	ALT \geq 5xULN but <8xULN and cannot be monitored weekly for \geq 2 weeks ALT \geq 3xULN but <5xULN and cannot be monitored weekly for \geq 4 weeks
Symptom ³	ALT \geq 3xULN associated with symptoms (new or worsening) believed to be related to liver injury or hypersensitivity
Necessary measures and assessment items for liver event	
Actions	Follow Up Assessments

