
 Immediately discontinue the administration of the investigational product. Report it to GSK within 24 hours. Complete the liver event CRF and complete an SAE data collection tool if the event also meets the criteria for an SAE². Perform liver event follow up assessments Monitor the participant until liver chemistries resolve, stabilize, or return to within baseline (see MONITORING below) Do not restart/rechallenge participant with study treatment unless allowed per protocol and GSK Medical Governance approval is granted If the resumption/re-administration of the investigational product is not stipulated in the protocol or approved by GSK's Medical Governance, the administration of the investigational product will be discontinued 	
 Viral hepatitis serology⁴ Obtain INR and recheck with each liver chemistry assessment until the transaminases values show downward trend Only in those with underlying chronic Hepatitis B at study entry (identified by positive Hepatitis B surface antigen) quantitative Hepatitis B DNA and Hepatitis delta antibody⁵ Serum creatine phosphokinase (CPK) and lactate dehydrogenase (LDH). Fractionate bilirubin, if total bilirubin \geq 2xULN Obtain complete blood count with differential to assess eosinophilia Record the appearance or worsening of clinical symptoms of liver injury, or hypersensitivity, on the AE report form Record use of concomitant medications on the concomitant medications report form including acetaminophen, herbal remedies, other over the counter medications.

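### Liver stopping is stated at two strengths: Section 8.2.1 asks the investigator to consider it, Appendix 6 orders it at once, and no sentence says which passage prevails

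*Protocol*

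**What the plan says.** All references are to the Amendment 2 text of the protocol.

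- **Section 8.2.1**, headed as stopping criteria: "The investigator should consider discontinuing the study treatment upon discovery of liver function test abnormal". The sentence applies "if the subject is applicable to any of the symptoms presented in the algorithm", or where the investigator thinks stopping is best for the subject. Two algorithms follow. The first is titled "Algorithm A: Phase III-IV Liver Chemistry Stopping and Increased Monitoring Algorithm"; the second covers closer monitoring with continued therapy. Under each stands a pointer: "Liver Safety Required Actions and Follow up Assessments Section can be found in Appendix 6".
- **Appendix 6** (Section 12.6) has a table titled "Criteria for discontinuation based on the liver function test values". The first action it requires when a criterion is met is: "Immediately discontinue the administration of the investigational product". On restarting it says: "Do not restart/rechallenge participant with study treatment unless allowed per protocol and GSK Medical Governance approval is granted".
- **Section 8.1** states that "treatment discontinuation shall not be defined in this study, and will be considered to be identical to subject withdrawal from this study".
- **Section 8.2.6** forbids resuming treatment in subjects withdrawn for hepatic test results, without exception.
- **Section 5.1.3.1** lists eight conditions for a further injection in the open-label phase. None refers to laboratory results; Amendment 2 removed them, on the ground that the product is unlikely to affect them.

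**The concern.** A stopping rule for safety should read the same wherever it appears. Here the section that an investigator would open first makes stopping a matter for consideration, and the appendix makes it an order. Because Section 8.1 turns discontinuation into withdrawal, the wording bears on whether a subject leaves the study or remains a candidate for further 400-unit injections. It also bears on how hepatic withdrawals are counted and on how many of the roughly 120 randomised subjects are among the roughly 100 expected to complete Week 48. Subjects with the same liver results could be handled differently at different sites because the sites read different pages.

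**Working it through.** The protocol states no figure on this point, so the check is a comparison of passages.

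**1. Do the two passages meet on the same results?** Appendix 6 has two tiers.

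- *Stop tier:* ALT at or above 8xULN; ALT 5 to below 8xULN for at least 2 weeks; ALT 3 to below 5xULN for at least 4 weeks; ALT at or above 3xULN with bilirubin at or above 2xULN (more than 35% direct), with INR above 1.5, or with related symptoms; and cases that cannot be monitored weekly.
- *Continue tier:* ALT 3 to below 8xULN, bilirubin below 2xULN, no related symptoms, weekly monitoring possible. It ends once a stopping criterion is met.

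In the continue tier, considering whether to stop conflicts with nothing. In the stop tier, Section 8.2.1 says consider and Appendix 6 says stop at once. The conflict is confined to the stop tier.

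**2. Is precedence stated?** No. Section 8.2.1 tells the reader where the required actions are, but not that they override its own sentence.

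**3. Do other references settle it?** No. The first footnote to Table 10 in Appendix 2 places the hepatic discontinuation criteria and follow-up in Section 8.1 and Appendix 6. The actions column of Appendix 6 also refers to follow-up prescribed in Section 8.1. That section is one paragraph equating discontinuation with withdrawal; it contains no hepatic criterion and no follow-up.

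**4. Is the restart wording aligned?** Not fully. One Appendix 6 bullet requires both protocol permission and sponsor governance approval; the next joins the two with *or*. Section 8.2.6 admits no restart.

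**5. What else would prevent a further injection in a subject kept in under Section 8.2.1?**

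- Section 8.2.6 reaches only subjects already withdrawn.
- ALT at or above 3xULN with the bilirubin or INR criterion must be reported as an SAE. If it is judged treatment-related, Section 8.2.3 calls for withdrawal and retreatment criterion 5 bars injection.
- For ALT at or above 8xULN alone, a persistent ALT rise, or a liver event judged unrelated, no retreatment criterion refers to the liver result. What remains is judgement: criterion 4 (400 units considered appropriate) and criterion 7 (no unacceptable safety concern, which names potential SAEs, ECG and pulmonary function).

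**6. How many subjects, and which endpoint?** The protocol gives no liver-event rate. Assuming 0% to 3% of 120 gives 0 x 120 = 0 to 0.03 x 120 = 3.6, that is 0 to 4 subjects. The exclusion of raised ALT at entry and the Amendment 2 rationale point to the low end. The schedule of activities places the first post-dose laboratory test at V5, Week 12, after the Week 6 primary assessment. A subject identified at V5 of Part 1 could have up to three further injections ahead (Parts 2, 3 and 4).

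**The case against.** The best defence is that the two passages can be obeyed together. Considering discontinuation does not license keeping a subject whom Appendix 6 orders stopped; only stopping satisfies both, and Section 9 allows no waivers. The sentence in Section 8.2.1 may also be a general introduction to two algorithms, one of which intends continued therapy, with Appendix 6 sorting the cases. The heading and the two pointers lead a careful reader to the appendix. The flow charts are missing from the available copy, and Algorithm A may itself order stopping.

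Much of this stands, and it rules out several stronger readings that a reader might infer:

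- *That sites could follow opposite rules without deviating.* A site that keeps a subject who meets a listed criterion breaches Appendix 6.
- *That one subject could be both withdrawn and kept.* The comparison is between subjects with the same results at different sites.
- *That nothing would block re-injection after any liver event.* Treatment-related liver SAEs are blocked by Section 8.2.3 and criterion 5.
- *That liver follow-up stops at withdrawal.* Appendix 6 requires monitoring until the tests resolve, stabilise or return to baseline.

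The defence does not remove the discrepancy itself. The sentence in Section 8.2.1 is tied to the conditions in the algorithm, the first algorithm is by title the stopping one, and the introduction reading has to be supplied by the reader. The QTc and pregnancy rules beside it are directive. A stop box in the unseen chart would sharpen the contrast with the sentence above it, not resolve it.

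**Conclusion.** The point holds in a limited form. One liver stopping rule is worded as discretionary in Section 8.2.1 and mandatory in Appendix 6, without precedence and with two references to a section that contains no such rule. The practical exposure is isolated or persistent ALT elevation and liver events judged unrelated, where the retreatment criteria leave only investigator judgement. The numbers are probably very small: 0 to 4 of 120 on an assumed rate of 0% to 3%, possibly none. The effect falls on subject safety and on consistent counting of withdrawals, mainly in the open-label phase. The Week 6 responder comparison is essentially unaffected, and no stated power figure depends on the completer count. The conclusion rests on the visible text; the algorithm charts could not be read. It takes no position on which liver rule is right.

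**What to change.** Reconcile the passages in one wording amendment:

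1. Make Section 8.2.1 and Appendix 6 state the same obligation for a subject who meets a listed criterion. This can be done by having Section 8.2.1 refer directly to the Appendix 6 actions, or by changing the appendix to match. Check the Algorithm A chart against the result.
2. Correct the references to Section 8.1 in the Table 10 footnote and in the Appendix 6 actions column.
3. Align the Appendix 6 restart wording with Section 8.2.6.
4. State in the same place whether such a subject is withdrawn in the sense of Section 8.1.

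Which rule applies is for the sponsor's medical team to decide. The cost is an amendment to a few sentences; sample size, visits and analysis do not change.

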8.2.2. QTc Stopping Criteria

- For a decision on a subject's eligibility or study discontinuation, the same method for correction of QT interval must be used in the subject throughout the study, and must not be changed once the subject is enrolled.
 - For instance, if a subject is enrolled based on QTcB, decisions on the subject's withdrawal must be made based on QTcB.
 - The method used for correction of QT interval pertinent to the enrollment of a subject must be used for all QTc data to be collected throughout the study for the data analysis on the subject; provided that such rule is not applicable to ECG intended to ensure safety and also ECG not defined in the protocol.
- QTc should be determined based on a single measurement of ECG or the mean of ECG measured at 3 timepoints in a short period of time (e.g., 5 to 10 minutes). If abnormality is detected in a single measurement, ECG should be measured again, this time, at 3 timepoints.
- The lowest value of QTc cannot be used for a decision to withdraw a subject.

Refer to the schedule of assessment (SoA), completion visit (FV), for the details of data to be collected at the discontinuation of study treatment. Discontinue this study if the mean ECG is applicable to any of the following conditions:

- QTc >500 msec or uncorrected QT >600 msec
- Change in QTc from baseline >60 msec

The following withdrawal criteria should be applied for subjects with bundle branch block:

Baseline for subjects with bundle branch block	Withdrawal criteria for subjects with bundle branch block
<450 msec	>500 msec
450 to 480msec	IJYO530 msec

8.2.3. Treatment discontinuation due to treatment-related SAE

A subject should be withdrawn from this study if treatment-related serious adverse event has occurred.

8.2.4. Treatment discontinuation due to pregnancy

A female subject who become pregnant during this study must be withdrawn from the study.

8.2.5. Withdrawal of subjects who start receiving prohibited medications or therapies

If a prohibited medication or therapy (See section 7.7.2.) needs to be started during the study, the subject must be withdrawn from this study; in which case, the subject must make the study completion visit (FV) before starting the prohibited medication or therapy.

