3.3.1. Risk Assessment

Important identified risks	Reports suggesting risks/ Outlines of rationale	Measures for risk minimization
Investigational product: GSK1358820		
Hypersensitivity	Serious and/or immediate hypersensitivity reactions (anaphylaxis, serum sickness, urticarial, soft tissue edema, or dyspnea, etc.) have been rarely reported.	Patients who previously experienced allergic reactions due to botulinum toxin type A, an additive agent of sodium chloride, or human serum albumin are excluded from enrolment. Upon written informed consent process, subjects will be explained that any urticarial, swelling face, throat swelling, wheezing, dizziness, or dyspnoea should contact their investigator.
Pre-existing neuromuscular disorder	Patients with neuromuscular junction diseases (myasthenia gravis, Lambert-Eaton myasthenic syndrome etc.) may increase the sensitivity to the product, resulting in excessive muscular weakness.	For patients with myasthenia gravis, Eaton-Lambert syndrome (ELS), amyotrophic lateral sclerosis, or a serious disease and who use a concomitant drug (s) which may inhibit neuromuscular function, exclusion criteria will be set, and those patients will be excluded from enrolment in the study (refer to 6.2.1).
distant spread of toxin	Adverse drug reactions in the remote muscles, except but the injected site, have been rarely reported. The adverse drug reactions include muscular weakness, constipation, dysuria, swallowing difficult, and non-accidental entering of food or fluid in the lungs not via the stomach, but the trachea (pneumonia may occur). The patients who received the product at a higher dose are considered likely to have increased risks for these adverse drug reactions.	In this study, a high dose of 400 units of the product will be injected. Therefore, the subjects will be followed up after 2, 4, 6, and 12 weeks of injection. The safety of the subjects will be observed carefully. Use of at least one of the following guide tools (electromyogram, electrical stimulator, or ultrasonography) will be essential in the blind phase to ensure identification of the exact site of injection.

Important identified risks	Reports suggesting risks/ Outlines of rationale	Measures for risk minimization

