9.2. Adverse events

Definitions of adverse events and serious adverse events (SAE) are as specified in Appendix 4. The investigator or a person assigned by the investigator is responsible for detecting, recording, and reporting events that match the definitions of adverse events and SAEs, and also, responsible for follow-up investigations on SAEs, as well as events related to the study drug or this study, and events that resulted in treatment discontinuation or subject withdrawal (See section 8).

9.2.1. Period subject to collection of data related to adverse events and SAEs, and the frequency of such data collection

- All SAEs will be collected from the start of treatment until Final Visit at the time points specified in the SoA (Section 2).
- All AEs will be collected from the start of treatment until Final Visit at the time points specified in the SoA (Section 2).
- Medical occurrences that begin before the start of study treatment but after obtaining informed consent will be recorded on the Medical History/Current Medical Conditions section of the case report form (CRF) not the AE section.
- All SAEs will be recorded and reported to the sponsor or designee within 24 hours, as indicated in Appendix 4. The investigator will submit any updated SAE data to the sponsor within 24 hours of it being available.
- Investigators are not obligated to actively seek AEs or SAEs in former study participants. However, if the investigator learns of any SAE, including a death, at any time after a participant has been discharged from the study, and he/she considers the event to be reasonably related to the study treatment or study participation, the investigator must promptly notify the sponsor.
- The method of recording, evaluating, and assessing causality of AEs and SAEs and the procedures for completing and transmitting SAE reports are provided in Appendix 4.

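### Routine collection of new adverse events stops at the withdrawal visit, so a subject withdrawn within 12 weeks of an injection leaves the 84-day safety window partly unobserved

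*Protocol*

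**What the plan says.** All references are to the current protocol text (Amendment 2).

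- Section 8.2.5: needing a therapy on the 7.7.2 list means withdrawal, and "the subject must make the study completion visit (FV) before starting the prohibited medication or therapy".
- Section 8.2: a subject who leaves for any reason "must visit the study site for study termination assessment promptly upon decision to discontinue the study".
- Section 8.1: the effect "sustains for about 3 to 4 months following a single dose". The protocol gives this as its reason for the rule that "treatment discontinuation shall not be defined in this study, and will be considered to be identical to subject withdrawal from this study".
- Section 9.2.1: "All AEs will be collected from the start of treatment until Final Visit", and the same holds for SAEs. Afterwards, "Investigators are not obligated to actively seek AEs or SAEs in former study participants"; an SAE that the investigator happens to learn of and judges related must still be notified.
- Section 3.3.1: on distant spread of toxin, "The patients who received the product at a higher dose are considered likely to have increased risks for these adverse drug reactions". One of the listed counter-measures is that "the subjects will be followed up after 2, 4, 6, and 12 weeks of injection".
- Section 10.3.2: AEs in the blinded period are summarised in two ways. One runs from the initial dose to the first open-label dose, or to study completion or withdrawal. The other covers the first 84 days after the initial dose and has no rule for subjects who leave earlier.

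**The concern.** An intramuscular depot dose cannot be stopped once it is given, so withdrawal ends observation but not exposure. The protocol has no status for a subject who receives no more injections but is still followed for safety. Prohibited therapy is only one route to this. The other section 8 withdrawals (liver chemistry, QTc, related SAE, pregnancy, investigator or subject decision) lead to the same prompt final visit and the same end to routine collection.

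At stake is the completeness of the fixed 84-day comparison of 400 with 240 units, and of the 12-week follow-up that 3.3.1 offers as protection at the higher dose. Subjects withdrawn early stay in the denominator while events that start after their final visit are not sought. No analysis can recover events that were never collected, so this has to be settled in the protocol and not in the analysis plan.

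**Working it through.** **Inputs.** Window: 84 days (10.3.2), equal to 12 weeks (5.1.3.1). Visits: Weeks 2, 4, 6 and 12. Planned size: 60 per group. Planned completion: 100 of 120 at Week 48 (10.1). The protocol gives no number for withdrawals within 12 weeks of an injection.

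**The plan's own figure.** Section 10.1 states a power of about 62% for 70% against 50% with 60 per group. The normal approximation gives 61.1% with pooled variance and 62.7% with unpooled variance, so it is reproduced. It does not enter this point.

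**1. Loss per subject.** Unobserved days = 84 − d, where d is the day of the final visit after the initial dose.

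- d = 14: 70 days (70/84 = 83%)
- d = 28: 56 days (67%)
- d = 42: 42 days (50%)
- d = 56: 28 days (33%)
- d = 70: 14 days (17%)
- d = 84 or later: none

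The same formula applies to the 12 weeks after each open-label injection, although those days lie outside the 84-day table.

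**2. Loss per group.** Planned person-time is 60 × 84 = 5,040 days. With k subjects withdrawn, the share lost is k × (84 − d) / 5,040. Taking k from 1 to 6 as an assumption:

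- 1 × 42 / 5,040 = 0.8%
- 3 × 56 / 5,040 = 3.3%
- 6 × 70 / 5,040 = 8.3%

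The top value is hard to reach. The plan allows for (120 − 100)/120 = 16.7% non-completion, about 10 per group, for all reasons over 48 weeks. If those losses were spread evenly (a further assumption), 10 × 12/48 = 2.5 per group would fall in the first 12 weeks. At an average loss of half the window, that is 2.5 × 42 / 5,040 = 2.1%. Some of these subjects would have withdrawn consent or been lost to follow-up, and no rule could recover their data.

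**3. Weight of one event.** 1/60 = 1.7 percentage points. As an illustration only, a true 3/60 (5.0%) with one event unseen would be reported as 2/60 (3.3%).

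**4. What is kept and what is lost after the final visit.**

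- Kept: SAEs already reported (9.2.3); events related to the drug or the study, and events that led to withdrawal, for which 9.2 makes the investigator responsible for follow-up; later SAEs judged related, if the investigator hears of them (9.2.1).
- Lost: active collection of any AE or SAE that starts after the visit, and the later course of non-serious AEs that are neither drug- or study-related nor the cause of withdrawal.

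**5. After the change.** If collection runs to 84 days after the last injection, the loss is 0 days for every withdrawn subject who still consents and can be reached.

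**The case against.** The best defence has four parts.

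First, 9.2 already requires follow-up of the events that matter most. An infection caused by toxin spread that led to a banned antibiotic would be both drug-related and the cause of withdrawal, so its course would be followed. This stands, and it confines the loss to the items listed as lost in the working.

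Second, withdrawal is foreseen: the other blinded-period AE summary in 10.3.2 ends there by design. That also stands, so the 84-day table is not the only blinded safety comparison. It does not complete the fixed window, which has no such rule. Section 5.4 is no contradiction either, because it seeks Week 48 safety evaluation only as far as possible.

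Third, a final visit before a confounding therapy is sensible, because several banned drugs act at the neuromuscular junction. Agreed; the order of events in 8.2.5 is not the defect.

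Fourth, direction. A reader might infer that AEs in the 400 units group are understated, since 3.3.1 expects more distant-spread reactions at a higher dose, names pneumonia among them, and 7.7.2 bans some antibiotics. The documents do not support that as a net direction. Much of the 7.7.2 list is alternative treatment for spasticity (nerve blocks, casts or splints, surgery, electrical stimulation), which could as well follow poor response in the 240 units group, whose elbow flexors receive placebo. Many of these interventions, if already planned, also exclude a patient at entry.

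A reader might also measure the gap against the 3 to 4 months of effect in 8.1. That is a duration of efficacy, not a promised safety follow-up: a subject who has all four injections is followed for only 12 weeks after the last. The proper yardstick is 84 days.

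**Conclusion.** The point holds as a minor, cheap improvement. The chain from withdrawal to final visit to the end of routine AE and SAE collection is explicit and covers all section 8 withdrawals, of which 8.2.5 is one instance. For a subject withdrawn in Part 1 at Day 14, 28 or 42, 83%, 67% or 50% of the 84-day window goes unobserved. For a group, the share depends on a count that the protocol does not give. Under the assumptions shown it runs from 0.8% to 8.3% of planned person-days, with the low end more plausible, and it may be zero. The direction of any bias between groups is unknown. The Week 6 primary result is not affected, and nothing here shows harm to a subject.

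**What to change.** Keep the final visit before the prohibited therapy where feasible, and give no further injections. Amend 8.1, 8.2.5 and 9.2.1, with a matching entry in the schedule of activities, along these lines:

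*For a subject withdrawn for any reason in section 8, AEs, SAEs and concomitant therapies continue to be collected, by visit or telephone, until 84 days after the last injection, unless consent is withdrawn or the subject is lost to follow-up.*

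Limiting the rule to withdrawn subjects leaves the visit timing of completers as it is.

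The cost is three short text changes and a schedule entry, plus at most four contacts per withdrawn subject (in place of V2 to V5), by telephone where suitable. The downside is attribution: AEs after a prohibited therapy may be due to that therapy and must be read against its start date. Section 7.7 already requires that date for drugs used during the study; the amended rule would extend its collection past withdrawal and to non-drug therapies.
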